8. TRIAL INTERVENTION

8.1 Description of Standard of Care

The management of lung transplant recipients both before and after the development of CLAD may vary subtly between the UK centres. However, the underlying principles are well aligned in terms of a standardised maintenance immunosuppression regime (cell cycle inhibitor, calcineurin inhibitor and corticosteroids) and prophylaxis against common viral, bacterial, and fungal infections with attention to blood pressure control, lipid profiles, preservation of renal function and bone protection. Acute cellular rejection of ISHLT grade A2 or higher is treated with short term augmentation of corticosteroids in all centres.

The diagnostic approach to new onset CLAD is also well aligned with the 2019 ISHLT criteria (3) with a diagnosis made only after a failed response to a trial of azithromycin therapy and exclusion of reversible causes such as cellular or humeral rejection, large airway anastomotic obstruction and infection. After a diagnosis of probable CLAD, patients are observed and those with progressive loss of lung function have traditionally been offered potential immunomodulatory therapy with either TLI or ECP depending on availability and funding. Other therapeutic approaches with little to no evidence to support them have generally been avoided. Retransplantation provides the only realistic therapeutic option in those who progress to very severe CLAD without significant other comorbidities.

All five centres participating in this trial have agreed clear principles for the SOC for CLAD treatment. The basis remains supportive with supplementary oxygen for hypoxia, prevention and treatment of infective exacerbations, physical rehabilitation, and psychosocial support. This will be the approach in both arms of the study with use of ECP in the treatment arm the only difference.

Participants will not be treated with any immunomodulatory interventions such as TLI or ECP as part of SOC in the trial. Only if there is rapidly progressive CLAD disease by 12 weeks as defined in the

protocol (>20% decline in FEV1 or FVC) will the patient leave the study and be eligible to access immunomodulatory interventions outside the study at the discretion of the clinical team. If at any point after 12 weeks, but before 24 weeks, they reach >20% decline in FEV1 then they will also have the option to leave the study and access immunomodulatory treatments at the discretion of the clinical team.

For more details of the agreed Standard of Care Pathway for the trial, please see Appendix 1 of this protocol.

8.2. Description of ECP Treatment

ECP therapy is performed using the THERAKOS™ CELLEX™ Photopheresis System® which is an automated enclosed system which separates a given volume of the patient's whole blood into plasma, red blood cell and white blood cell fractions. The red cells and some of the plasma is immediately returned to the patient while the white cells and remaining plasma is collected in a separate chamber. This collection process is repeated over a number of cycles. The buffy coat suspension of white blood cells is then treated with the photosensitising drug methoxsalen. After the cells have absorbed this drug, they are exposed to UVA light radiation, and then returned back into the patient's body. THERAKOS™ have agreed to provide CELLEX™ System Procedural Kits at a discounted rate to sites for trial procedures. Sites are also able to loan a CELLEX™ system from THERAKOS™ if required to meet ECP capacity as a result of trial recruitment.

In this trial, UVADEX® (methoxsalen) Solution will be the investigational drug. UVADEX® (methoxsalen) Sterile Solution will be injected directly into the Recirculation Bag of the extracorporeal circuit after completion of the buffy coat collection, immediately prior to initiating photo-activation. The dose of UVADEX® used to inoculate these cells will be calculated based on the standard treatment volume formula (see section 8.6). Heparin is the standard anticoagulant for use with the THERAKOS™ CELLEX™ Photopheresis System®. However, sites may use other anticoagulants such as citrate if routinely used as part of their standard local ECP protocol or if heparin is contraindicated for a patient. Patients in the ECP arm should have all of their treatments with the THERAKOS™ CELLEX™ Photopheresis System® at a set frequency over the course of 24 weeks. Each treatment takes about 2-3 hours to complete, and each cycle consists of 2 treatments performed on consecutive days. The treatment schedule in the study protocol means patients randomised to the ECP arm must receive their first cycle ideally within 14 days of their baseline visit, but no later than 28 days after baseline visit. Cycles are then performed every 2 weeks for the first 12 weeks and then every 4 weeks for the next 12 weeks. By 24 weeks after the baseline visit those who complete the study will have received 9 cycles of ECP equating to 18 individual treatments.

8.2.1. Venous and Central Access for ECP treatment

IV access will be required for the administration of the ECP treatment via the THERAKOS™ CELLEX™ Photopheresis System. This should be provided in line with each sites' local procedures for the delivery of ECP treatment.

8.2.2. Peripheral Venous Catheters

If possible, it is preferable to administer the ECP treatment via peripheral venous access, to minimise the risk of infection. In single needle mode, the access device must be capable of withstanding the

negative pressures required to collect whole blood and the positive pressure used to return blood components.

In double needle mode, it may be possible to use a large gauge device for drawing and a smaller gauge device for return. It is recommended that more than one type of venous access device be available. Choose the one most suitable for the patient undergoing treatment.

For peripheral venepuncture, the following devices are suitable for peripheral access:

- 16G, 17G Fistula Needles DRAWING or RETURNING
- 17G, 18G IV Catheter (High durometer angiocatheter) drawing or returning
- 20G IV Catheter (High durometer angiocatheter) returning

8.2.3. Central Venous Catheters (CVC)

When peripheral venepuncture is not possible, alternative devices such as long-term indwelling catheters, temporary catheters, or subcutaneous ports may be used providing they meet the requirements below. Careful planning to ensure the appropriate device is implanted will prevent failed or shortened ECP therapies due to access failure.

Any catheter intended to be used with the THERAKOS™ CELLEX™ Photopheresis System must be able to withstand the negative pressure of the peristaltic pressure pumps without collapsing and they must provide a flow rate of at least 15 mL/min. Overall requirements are:

- Minimal internal diameter of 3.0 mm or 9FR. (1 mm = 3 French)
- Maximum length of 36 cm
- High durometer or stiffness of catheter (designed for haemodialysis or apheresis procedures to provide high flow output).

It may be necessary to replace a central venous catheter if it stops working or becomes blocked. This is at the discretion of the treating clinician and should be fully documented in the participant record, along with any impact that has on the ECP treatment, if appropriate.

Participants who have a CVC inserted to receive ECP therapy in the trial must be educated on the self-care requirements and signs of infection to look out for. Maintenance of CVC integrity such as exit site dressings and patency via regular flushes should be performed in line with local site policies.

8.2.4. Other access options

It may also be possible to administer the ECP via the THERAKOS™ CELLEX™ Photopheresis System using implanted venous access devices. However, please note that subcutaneous ports designed specifically for high-speed infusions will not provide adequate output for drawing. Implant only ports designed for both high-speed input and output are required.

The THERAKOS™ CELLEX™ Photopheresis System is also capable of both drawing from and returning to an AV Fistula or shunt. Centre-specific guidelines should be followed for accessing and maintaining the graft.

8.3. Name and Description of IMP

The participants in this trial will be randomised in a 1:1 ratio to receive either standard care plus UVADEX® (methoxsalen) solution as part of their ECP treatment, or standard care alone.

UVADEX® is clear, colourless to pale yellow solution, which is used for blood fraction modification. Each vial of UVADEX® contains 10ml of methoxsalen at a concentration of 20 micrograms/ml, giving a total of 200 micrograms per vial.

The other ingredients are Propylene Glycol, Ethanol 95%, Glacial Acetic Acid, Sodium Acetate Trihydrate, Sodium Hydroxide, Sodium Chloride and Water for Injections.

An SmPC will be used for the UVADEX® medication and should be referred to for further information.

8.4. Drug Storage and Supply

UVADEX® can be stored at room temperature but should not be stored at temperatures exceeding 25°C. No formal trial specific temperature monitoring will be required for the IMP. Standard hospital procedures for storing and managing medications will be followed.

UVADEX® will be prescribed by a suitably designated trial clinician and obtained via usual means from the hospital pharmacy or ward supplies for use on the ECP unit. Supplies should be obtained from standard NHS Hospital stock. No IMP will be provided by Sponsor. Used vials of UVADEX® solution will be destroyed locally following administration in accordance with local procedures. Accountability will be performed by the trial management team via collection of batch number, expiry date and dose given within the eCRFs.

8.5 Preparation and Labelling of IMP

Preparation of the UVADEX® prior to use with ECP is covered in section 8.6. There is no requirement for sites to label the product with Annex 13 compliant labels.

8.6 Dosage Schedule & Modifications

Participants randomised to ECP treatment will receive UVADEX® treatment up to 18 times (9 cycles) as part of the trial. The time points for the treatments are shown in the schedule of events in section 5.4.1. Each treatment will take place on two consecutive days.

During each photopheresis treatment, plasma and leukocyte enriched blood are obtained by centrifugation and collected into a photoactivation bag. The treatment volume (which is displayed on the display panel of the instrument) is then used to calculate the dose of UVADEX® required using the formula:

Treatment volume x 0.017 ml of UVADEX® for each treatment
For example: Treatment volume = 240 ml x 0.017 = 4.1 ml of UVADEX®

The dose of UVADEX® required will be different for each treatment for each participant.

The prescribed amount of UVADEX® will be calculated, as per the formula above, drawn from the single 10 ml vial and injected into the recirculation bag prior to the photoactivation phase. The leukocyte rich blood in the recirculation bag is then exposed to UVA light in a photoactivation chamber and re-infused into the participant. UVADEX® should be injected into the recirculation bag as soon as possible after withdrawing from the vial into a syringe to reduce the time the UVADEX® is in contact with the syringe. If the UVADEX® is exposed to a plastic syringe for longer than 1 hour it should be discarded.

8.7 Known Drug Reactions and Interactions

Methoxsalen has been shown to act primarily as a potent inhibitor of hepatic microsomal oxidative metabolic processes, including, but not limited to, CYP1A2, 2A6 and 2B1. Thus, it is to be expected that interactions will occur between methoxsalen and other medicinal products whose metabolism involves the hepatic cytochrome P450 system. The clearance of caffeine and antipyrine have been shown to be markedly reduced after methoxsalen treatment. Therefore, consumption of other P450 substrates may result in an extended half-life of methoxsalen, and consequently lead to prolonged photosensitivity and thus requiring continued precautions against exposure to sunlight beyond 24 hours following photopheresis treatment.

Studies have shown that methoxsalen also decreases the metabolic activation of paracetamol in animals and humans, probably because of methoxsalen-associated inhibition of hepatic cytochrome P450 oxidative transformation of paracetamol.

8.8 Concomitant Medications

All concomitant medications required for the standard care of the participants with CLAD will be allowed at the discretion of the investigator. A complete listing of all concomitant medication, including applicable contraceptive methods and vaccinations, received during the data collection period should be recorded in the eCRF and participant medical records. Concomitant use of methoxsalen and tolbutamide may lead to enhanced photosensitivity.

Special care should be exercised in treating patients who are receiving concomitant therapy (either topically or systemically) with known photosensitising agents. Such agents include fluoroquinolones, furosemide, nalidixic acid, phenothiazines, retinoids, sulphonamides, sulfonyleureas, tetracyclines, thiazides and voriconazole or other azoles associated with photosensitivity.

8.9 Assessment of Compliance

Compliance with the ECP / IMP regimen will be recorded in the participant medical records and in the eCRF.

9. PHARMACOVIGILANCE

9.1 Definitions

Term	Definition
Adverse Event (AE)	Any untoward medical occurrence in a participant to whom a medicinal product has been administered, including occurrences which are not necessarily caused by or related to that product.
Adverse Reaction (AR)	
An untoward or unintended response in a participant to an investigational medicinal product which is related to any dose administered to that participant.
 
The phrase “response to an investigational medicinal product” means that a causal relationship between a trial medication and an AE is at least a reasonable possibility i.e. the relationship cannot be ruled out.
 
All cases judged by either the reporting medically qualified professional or the Sponsor as having a reasonable suspected causal relationship to the trial medication qualify as adverse reactions

Reference Safety Information (RSI)	The RSI is a list of medical terms detailing the ARs that are expected for an IMP and must be referred to when assessing a SAR for expectedness.
Serious Adverse Event (SAE)	
A serious adverse event is any untoward medical occurrence that:
 
 • Results in death • Is life-threatening* • Requires inpatient hospitalisation or prolongation of existing hospitalisation • Results in persistent or significant disability/incapacity • Consists of a congenital anomaly or birth defect • Other important medical events that jeopardise the participant or require intervention to prevent one of the above consequences 
*Life-threatening refers to an event in which the participant was at immediate risk of death at the time of the event; it does not refer to an event which hypothetically might have caused death if it were more severe.

Serious Adverse Reaction (SAR)	An adverse event that is both serious and, in the opinion of the reporting Investigator, believed with reasonable probability to be due to one of the trial treatments, based upon the information provided.
Suspected Unexpected Serious Adverse Reaction (SUSAR)	A serious adverse reaction, the nature and severity of which is not consistent with the approved Reference Safety Information.

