1.2 Rationale

A systematic review using full text search terms for [ECP] + [lung transplantation] or [CLAD] or [BOS] or [RAS] in PubMed yielded 5 reviews, 2 mechanistic studies and 9 relevant clinical studies. These studies used ECP in lung transplant recipients with CLAD and showed promise in slowing or halting its progression (11). However, these are universally single centre retrospective studies conducted over prolonged periods of time while other aspects of care were also evolving. There was a lack of proper untreated controls and ECP was offered to only selected patients with CLAD. None of these studies were performed in the UK in an NHS setting, so high-quality evidence of the efficacy of ECP in CLAD treatment has not yet been established. The proof of concept for use of ECP in CLAD comes from 4 larger studies (described below) that represent a collective experience of 223 lung transplant recipients with CLAD, including RAS and BOS phenotypes. Of the 4 studies, 3 reported a clinical response ranging from 54–61%. None were conducted as a prospective randomised controlled trial (RCT) and all have limitations of bias in patient selection.

Morrell et al (12) reported retrospective outcomes on 60 patients treated with ECP for progressive BOS. They compared rate of decline in FEV1 for 6 months before and after commencement of ECP showing a significant reduction in the rate from -116 mls/month to -28.9 mls/month ($p=0.0001$). 25% of treated patients showed an increase in lung function within 6 months. There was a 13% rate of hospitalisation for line sepsis, including 1 death, but this was limited to only those with long-term indwelling apheresis catheters; no line infections were reported in those treated through peripheral cannulation. There was no control group and selection of patients for treatment implied bias.

Jaksch et al (13) reported a single centre experience of treating 51 BOS patients with ECP. 61% of those treated demonstrated improvement or stabilisation in FEV1 defined as <5% decline over the first 6 months of treatment. ECP treatment response was also associated with an improved survival and reduced need for retransplantation compared to patients with BOS not getting ECP and those not responding to ECP. There was a selection bias as only 26.2% of BOS patients at this centre received ECP. No adverse events (AEs), including serious infections, were reported.

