5.2.4 Research Specific Assessment

The following research assessments will be carried out at baseline;

- Full Pulmonary Function Tests (PFT):
 - Spirometry comprising FEV1 and FVC.
 - Flow Volume Loop including FEF25-75
 - Static Lung volumes comprising Total Lung Capacity (TLC) and Residual Volume (RV).
 - Total diffusing capacity (DLCO), alveolar volume (Va) and volume corrected diffusing capacity (KCO).
 - Pulse oximetry at rest.
- Research blood samples
 - 1 x 6ml lithium heparin tube
 - 2 x 4ml serum tubes
 - 1 x 3ml RNA tube

(see section 5.4.4 and E-CLAD UK laboratory manual for processing and storage information)

- 6MWT

- To prevent any delays in initiating ECP (should the participant be randomised to that arm) assess suitability of venous access at baseline visit and determine if peripheral cannulation is possible or whether a central venous catheter may be required

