9.2 Recording and Reporting AEs and SAEs

Adverse Events:

All AEs occurring from the time of consent to end of trial participation, must be recorded in the AE eCRF page as well as the participant's medical notes.

Events which are due to the symptomatic deterioration of the participant, and which are expected for participants who have CLAD progression, do not need to be reported as AEs. These events will be recorded in the participant record and will be reported in the eCRF, but not as AEs.

All adverse events which are not associated with the deterioration of the participant or their non-response to treatment will be recorded as AEs, both for participants in the ECP treatment group and also for those in the SOC group. These events include the following:

- Transient fever
- Transient hypotension
- Dizziness / Pre-Syncope
- Nausea
- Vomiting
- Loss of appetite
- Headache
- Fatigue
- Minor photosensitivity reactions
- Local site infections associated with peripheral or central venous catheterisation
- Other Infections of all types: Bacterial Fungal Viral
- Worsening of any baseline medical condition eg hypertension, diabetes, gastro-oesophageal reflux
- Need for blood transfusion
- Need for platelet transfusion

This list is not exhaustive and any other AE which, in the opinion of the investigator is not due to the progression of CLAD, should be reported as an AE.

Serious Adverse Events and Serious Adverse Reactions:

All SAEs occurring from point of consent to end of trial participation (end of the last trial related assessment) must be reported to NCTU on an SAE form and recorded in the AE eCRF page and recorded as serious.

All SARs occurring from the time of first ECP treatment up until the last trial related assessment for the participant at week 24 must be reported to NCTU on an SAE form and also recorded in the AE eCRF page and recorded as serious. All participants in the ECP arm must be followed up for a minimum of 4 weeks after the last ECP treatment.

Following this defined active monitoring period for SARs, investigators are still required to report any SARs or SUSARs they become aware of for all trial participants for the duration of the study (i.e. up until LPLV).

An unscheduled hospitalisation, with any of the following causes, will need to be reported as an SAE:

- Systemic infection associated with central venous catheter use
- Systemic infections associated with peripheral cannulation
- Sepsis of any cause
- Pulmonary embolus

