9.3 Reference Safety Information

The approved Reference Safety Information (RSI) is:

- Section 4.8 of the Uvadex 20 micrograms/ml Solution Summary of Product Characteristics (SmPC) dated 25/08/2021.

The SmPC is available via MHRA website: <https://products.mhra.gov.uk/>

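### Section 9.1 ties an adverse reaction to methoxsalen but a serious adverse reaction to the trial treatments, so harms of the ECP procedure have no consistent relatedness label

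*Protocol*

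**What the plan says.** The treatment under test is ECP as a whole, added to standard of care (section 2.1). Section 8.2 describes an automated extracorporeal procedure with blood separation, an anticoagulant (heparin as standard), methoxsalen and UVA exposure. Sections 8.2.1 to 8.2.4 cover venous access, including central lines. Only one component is the investigational product: section 8.2 says that UVADEX (methoxsalen) "Solution will be the investigational drug".

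Section 9.1 then sets the safety terms:

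- An AR is "An untoward or unintended response in a participant to an investigational medicinal product which is related to any dose administered to that participant". Its explanatory note asks whether "a causal relationship between a trial medication and an AE is at least a reasonable possibility".
- A SAR is a serious event "believed with reasonable probability to be due to one of the trial treatments".
- The reference safety information is described as a list of reactions expected for an IMP, to be consulted when a SAR is assessed. Section 9.3 fixes it as "Section 4.8 of the Uvadex 20 micrograms/ml Solution Summary of Product Characteristics (SmPC"), and section 9.4 applies it to the expectedness assessment.

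On timing, section 9.2 requires AEs and SAEs from consent to the end of participation. "All SARs occurring from the time of first ECP treatment" up to the last week 24 assessment form the active SAR period. After that, investigators must still report SARs and SUSARs that come to their notice, until the last patient's last visit.

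**The concern.** A serious reaction should be a subset of all reactions. Here the two rows attach causation to different objects, the drug in one and the trial treatments in the other. For most drug trials the difference would not matter. In this trial several plausible harms come from the procedure and not from methoxsalen: catheter infection, bleeding on circuit anticoagulant, hypotension from volume shift.

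The protocol itself shows that such harms are relevant. Of one retrospective ECP series of 60 patients, section 1.2 reports: "There was a 13% rate of hospitalisation for line sepsis, including 1 death". That figure is context only. It comes from a single uncontrolled series, and the infections were confined to long-term indwelling catheters, with none reported after peripheral cannulation.

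At stake is whether the treatment-related counts mean the same thing across five sites, and whether a reader of those counts can tell drug harm from procedure harm.

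**Working it through.** No figure in the protocol bears on this point, so there is no arithmetic. The check applies the section 9.1 and 9.2 wording to the kinds of event that ECP can cause. The broad reading takes trial treatments to mean the whole ECP procedure. The narrow reading takes it to mean the IMP.

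| Event caused by the procedure, not by methoxsalen | Recorded as AE or SAE? | AR? | SAR, broad reading | SAR, narrow reading |
|---|---|---|---|---|
| Non-serious line-site infection, or transient hypotension from volume shift | Yes, both listed in 9.2 | No | Not serious | Not serious |
| Serious line sepsis between cycle 1 and week 24 | Yes, listed | No | Yes, tested against Uvadex information | No |
| Serious bleed on circuit anticoagulant during a session | Yes, the list is not exhaustive | No | Yes, tested against Uvadex information | No |
| Serious complication of a line placed before cycle 1 | Yes, SAEs run from consent | No | Meets the definition but precedes the stated SAR window | No |
| Serious line infection after the last trial assessment | Not required | No | Reportable if the investigator becomes aware | Not reportable |

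The rows show the following:

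1. The AR column is No throughout, because the AR row requires a relation to a dose of the IMP.
2. The two SAR columns differ in every serious row. Under the broad reading an event can be a SAR without being an AR. Under the narrow reading it is neither.
3. Section 9.2 collects causality for each SAE but does not say causality to what, so the form description does not settle which reading applies.
4. In the last row the reading decides whether a report is due at all. In the other rows it changes the label only.
5. The start of the SAR window matters only in the fourth row. That row rests on an inference. Section 5.2.4 asks staff to "assess suitability of venous access at baseline visit and determine if peripheral cannulation is possible or whether a central venous catheter may be required", in order to avoid delay in starting ECP, but no section says when a line is inserted. Nor does the protocol say when lines are removed, so the last row is likewise a possibility and not a stated plan.

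**The case against.** The strongest reply is that no safety data are lost during participation. AEs and SAEs are recorded from consent, and AE recording expressly covers both arms. Section 9.2 names catheter and cannula infections, sepsis, hypotension, transfusion and failed vascular access. Serious events are reported within 24 hours with a causality judgement. Section 10.2 takes the safety population as everyone recruited. Line sepsis can therefore be counted by arm whatever its relatedness label. All of this stands, and it limits the point to classification and late reporting.

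A reader might infer that the SAR window excludes anticoagulant or blood-volume harms. It does not: those arise during ECP and so fall inside it. A serious line complication before cycle 1 is also still reported as an SAE.

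A reader might also infer that the definitions will make ECP look safer than it is. The documents do not show that. Under the broad reading serious procedure harms are SARs. Nothing restricts the final report or the committee reviews to related events. The expectedness rule can even push the other way, since a procedure-related SAR absent from the Uvadex list would be a SUSAR and so be expedited. Section 4.8 of that product information is not reproduced, so which procedure effects it lists cannot be checked.

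Nor does the 13% figure measure the defect. Section 8.2.2 prefers peripheral access to limit infection, and two other series cited in section 1.2 reported no adverse events or no significant complications. What remains unanswered is that two adjacent definitions conflict on the scope of the treatment.

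**Conclusion.** The inconsistency is real and stands on the face of section 9.1: an AR concerns methoxsalen, while a SAR concerns the trial treatments. Its effect is confined to two things. AR, SAR and SUSAR counts may differ between investigators who read the same words differently. And after the active monitoring period the duty to report a procedure harm depends on that reading. All-cause AE and SAE comparisons by arm are unaffected.

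The number of events concerned cannot be derived, because the protocol gives neither the expected share of patients with central lines nor their removal times. The conclusion assumes that the AE and SAE forms, which are not shown, do not already separate drug from procedure causality. If they do, only the wording of section 9.1 and the timing in 9.2 need attention. This is a low-cost improvement in safety attribution, not a threat to the trial's safety data.

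**What to change.** - Give the AR and SAR rows in section 9.1 the same scope, in the same words.
- For each AE and SAE in the ECP arm, record relatedness twice: (a) to methoxsalen; (b) to the ECP procedure, meaning venous access including line insertion, anticoagulant, circuit and volume shift, and the UVA device.
- Assess (b) from randomisation, so that a line complication before cycle 1 is covered.
- Apply the Uvadex reference safety information to (a) only.
- State in section 9.2 whether the duty to report after the active period covers (a), (b) or both.
- Tabulate (a) and (b) for the data monitoring committee, the annual safety report and the final report.

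The cost is about one extra field on the AE eCRF and SAE form, plus wording in sections 9.1 to 9.3. More events will be labelled ECP-related, so the reported profile may look somewhat less favourable. Treatment, endpoints and sample size do not change.
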